6.1.2 Secondary study parameters/endpoints

For this study there are multiple secondary study parameters:

QoL caregiver:

The quality of life of the caregiver will be evaluated at every time point using the Caregiver Reaction Assessment (CRA). The CRA is a feasible and reliable instrument for determining the burden of caregivers of cancer patients which includes both negative and positive aspects [40].

Nutritional intake:

Nutritional intake will be evaluated at every time point based on a 3-day food diary filled in by the patient. The food diary will be cross checked by a dietician and, if necessary, the patient will be called for clarification. The food items will be coded and calculated according to the Dutch Food Composition Table (NEVO, RIVM).

Nutritional status:

Nutritional status will be assessed using the handgrip method with the JAMAR handgrip measurer at every time point. Hand grip strength serves as a predictor for the overall muscle strength and functional status [41, 42] For reliable results, two consecutive measurements alternating both hands will be recorded with patients sitting in an upward position and the arm in a 90-degree angle. The validated Patient Generated- Subjective Global Assessment (PG-SGA) will also be used to determine the nutritional status and will be filled in by the AYA's/research assistants in consultation with the patient at every time point [43].

Performance scale:

The Karnofsky Performance Status Scale is used to summarize the ability of patients to perform daily activities and the degree of dependence on help to do so. This status is based on 11 levels and ranges from 0, indicating death, to 100, indicating no complaints or evidence of disease [44]. This score will be determined in consultation with the patient at every time point. Physical performance will also be assessed by the Short Physical Performance Battery (SPPB). This is a frequently used test to measure functional status and physical performance. It consists of three lower

extremity physical performance measures: standing balance, gait speed and chair rises (sit-to-stand) [45].

Medication use:

Medication use will be evaluated at every time point by obtaining information from the medical file of the patients. Information will be cross-checked by the researcher on doses and frequency of medication use. During the intervention period, medication use will be assessed by asking patients to log on a diary when they used which medication including dosage.

Symptoms:

To assess the number and the severity of symptoms experienced by the patients, they are asked to fill in the 'Utrecht Symptoom Dagboek' every day for 3 weeks during the intervention period. This is a diary based on the ESAS which consists of 12 symptoms which are frequently experienced by palliative cancer patients [46]. On a scale from 0 to 10, patients can score the severity of the symptoms with 0 indicating no symptom and 10 indicating the worst possible symptom.

Patient satisfaction:

The Net Promoter Score (NPS) with additional questions will be used to assess patient satisfaction in the intervention group at time point 3. The NPS is determined by asking the question: 'How likely is it that you would recommend FoodforCare to a friend or colleague?'. The score ranges from 1-10 and patients can be grouped in 'promoters' (9-10 grading), 'passively satisfied' (7-8 grading) and 'criticasters' (0-6 grading). The NPS is finally calculated by subtracting the percentage of criticasters from the percentage of promoters [47]. Additional questions about satisfaction with respect to the food supply and logistics of FoodforCare at Home will be answered by the patients to explain their score. The control group will also receive a questionnaire about their wellbeing and way of shopping and cooking. Both questionnaires are self-composed and based on validated questionnaires because there is no Dutch validated questionnaire available about a home-delivered meal service.

During the pilot study, participants in the intervention group are asked to participate in an in-depth interview instead of the questionnaire. This interview will be led by one of the researchers. It will generate information about the home-delivered meal service so it can be improved when implemented in the RCT.

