2. OBJECTIVES

Primary objective:

To study whether FoodforCare at Home is superior to usual care with respect to quality of life in advanced abdominal cancer patients undergoing chemotherapy.

Secondary objectives:

1. To reduce diet-related symptoms in these patients by using FoodforCare at Home compared to usual care.
2. To improve nutritional intake (adequate protein and energy intake) in these patients by using FoodforCare at Home compared to usual care.
3. To improve the nutritional status of these patients by using FoodforCare at Home compared to usual care.
4. To improve the functional status of these patients by using FoodforCare at Home compared to usual care.
5. To reduce medication use for the purpose of treating diet-related symptoms in these patients by using FoodforCare at Home compared to usual care.
6. To improve quality of life of the partners/caregivers of these patients by using FoodforCare at Home compared to usual care.
7. To improve patient satisfaction towards nutrition in these patients by using FoodforCare at Home compared to usual care.

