5. INVESTIGATIONAL PRODUCT

5.1 Name and description of investigational product(s)

In a period of 1.5 year, 164 patients will be randomized into two groups. The intervention group will receive meals from FoodforCare at Home and the control group will continue their usual diet for 3 weeks. The FoodforCare at Home concept consists of five to six small protein and energy enriched meals that will be delivered twice a week. After an individual intake, the composition of the dishes will be tailored to the needs of the patient in terms of composition, diet, taste, flavor and portion size. Besides the meals, patients in the intervention group will also receive an information leaflet about the importance of protein during treatment and how to reach their protein requirements. The control group has no restrictions to their diet. The dishes are prepared every day by Maison van den Boer.

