5.4 Dosages, dosage modifications and method of administration

The composition of the FoodforCare at Home dishes are developed to enable maintenance and if possible improvement of the nutritional status of the patient. Therefore, a number of basic principles are chosen which are described below.

The aim is to stimulate protein intake as much as possible in order to maximize protein synthesis during treatment. Protein intake of at least 1.2 g/kg body weight is recommended for cancer patients [36]. On average, this is equivalent to an intake of 90-95 grams of protein per person per day (assuming an average weight of 75-80 kg). Protein intake of 20-25 grams per meal would ensure optimal postprandial protein synthesis in the muscles [37]. This and other information about the protein content of the FoodforCare products will be spread to the patients in order for them to make decisions that contribute to their protein requirements.

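### Diary coding names only the generic Dutch food table and no nutrient source for the enriched, tailored trial dishes, so protein and energy intake around T3 may be misestimated, mainly in the meal arm

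*Combined protocol and SAP*

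**What the plan says.** Secondary objective 2 (Section 2) is "To improve nutritional intake (adequate protein and energy intake) in these patients by using FoodforCare at Home compared to usual care". Section 6.1.2 sets out the measurement: "Nutritional intake will be evaluated at every time point based on a 3-day food diary filled in by the patient". The quality check is "The food diary will be cross checked by a dietician and, if necessary, the patient will be called for clarification". The conversion to nutrients is "The food items will be coded and calculated according to the Dutch Food Composition Table (NEVO, RIVM". No other composition source appears in the document.

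The intervention (Section 5.1) "consists of five to six small protein and energy enriched meals that will be delivered twice a week". The same section makes the dishes individual: an intake interview comes first, and composition and portion size are then adapted to each patient. Controls keep their usual, unrestricted diet.

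Section 5.4 shows that some product data exist: "information about the protein content of the FoodforCare products will be spread to the patients". The stated purpose is to help patients choose. Nothing connects these data to diary coding.

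Section 8.3 analyses nutritional intake as a continuous outcome, in the same way as the primary endpoint: a mixed model with a between-group comparison.

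**The concern.** The treatment under test is food that departs from ordinary composition, and the only stated nutrient source is a table of general foods. If a coder meets a trial dish in a diary and picks the nearest ordinary entry, part or all of the enrichment goes uncounted. Controls mostly eat food of the kind such a table describes. The error would therefore differ between arms, and randomisation does not remove an error that arises after allocation because of the treatment itself.

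At stake is the intake contrast. The plan expects better intake to lead to better nutritional status (Sections 1 and 5.4) and cites an earlier regular-food study in which protein intake rose without a gain in physical performance (Section 5.2). To read a similar or opposite pattern here, intake on trial meals has to be measured properly. If meal-arm intake is understated, a real increase could look small or absent.

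**Working it through.** **1. The plan's own protein figure (Section 5.4).** The recommendation is 1.2 g/kg at an average weight of 75-80 kg:

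- 1.2 × 75 = 90 g/day
- 1.2 × 80 = 96 g/day

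The stated 90-95 g/day reproduces, with the upper end rounded. It is a recommended total intake, not the amount that the dishes supply. It serves below only as a scale.

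**2. Which diaries can be affected.** The four time points are those of Table 1.

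| Time point | Can the diary contain trial meals? |
|---|---|
| T1, before chemotherapy | No: before randomisation |
| T2, at the 2nd cycle | Possibly: meals start with this cycle; the diary days are not specified |
| T3, at the 3rd cycle | Yes, if the diary days fall in the three-week meal period; the plan does not say |
| T4, three months after T3 | No: meals are not continued (Section 9.5) |

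The on-treatment contrast therefore rests essentially on T3.

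**3. Size of the error on an affected day.**

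Understatement (g/day) = D × s × m

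- D = daily protein, 90-95 g (Section 5.4).
- s = share of daily protein that comes from trial dishes. Not in the documents; assumed 25% to 100%.
- m = fraction of dish protein that the generic code misses. Not in the documents; assumed 10% to 30%.

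| s | m = 10% | m = 20% | m = 30% |
|---|---|---|---|
| 25% | 2.25-2.4 | 4.5-4.75 | 6.75-7.1 |
| 50% | 4.5-4.75 | 9.0-9.5 | 13.5-14.25 |
| 100% | 9.0-9.5 | 18.0-19.0 | 27.0-28.5 |

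The range is about 2 to 29 g/day. On the plan's own scale, a patient truly at 1.2 g/kg with s = 50% and m = 20% is recorded at 1.2 × (1 − 0.5 × 0.2) = 1.08 g/kg, below the recommendation.

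**4. The two other outcomes.**

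- Ingredient-level coding of the actual recipe: m = 0, so the error is 0.
- A generic match 10% too rich (m = −10%): overstatement from 90 × 0.25 × 0.10 = 2.25 to 95 × 1.00 × 0.10 = 9.5 g/day.

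Energy would follow the same formula, but the documents give no daily energy figure to put into it.

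**5. Reach.** Section 4.4 sizes the trial on the quality-of-life score alone. Diary coding does not enter that score or the calculation.

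**The case against.** The strongest reply is that the protocol nowhere says a trial dish will be coded as its ordinary counterpart. A dietician could enter each dish by ingredient, using values from the same national table, and that would count the enrichment. This is correct, and it is why no bias can be asserted as fact. But ingredient-level coding needs the recipe of the dish as prepared for that patient. The diary is filled in by the patient, and the only stated remedy for an unclear entry is a call to the patient. The plan does not route the supplier's recipe or the intake record to the coder. The favourable reading thus depends on a step that the plan leaves out.

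A reader might also infer that intake is understated in the meal arm only. The documents do not support that, for two reasons:

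- **Direction.** The dishes are small and portion size is tailored. If gaps were filled with standard portions or a rich generic match, intake could be overstated. Downwards is the more probable direction for enriched food matched to ordinary food, but it is not certain.
- **Arm.** Controls have no dietary restrictions and may eat enriched products, and a generic table also has error for home cooking. Mainly the meal arm is as far as one can go.

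It is also fair to say that intake is one of seven secondary objectives and that Section 8 plans no mediation analysis. Any wrong conclusion about whether a quality-of-life effect ran through intake would be a matter of informal interpretation.

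Finally, Section 5.4 mentions protein content only. It does not show that energy values, or the composition of each tailored dish, are already available.

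**Conclusion.** The point holds as a gap in a stated measurement rule. The plan names one generic nutrient source for all diary items and none for dishes that are enriched and individually composed. If those dishes are matched to generic foods, protein and energy intake is likely to be misestimated, probably downwards, mainly in the meal arm, and only on diary days with trial meals.

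The size cannot be determined from the documents. The 2 to 29 g/day range rests wholly on the assumed values of s and m and on using the recommended intake as the scale; zero and a reversed sign both remain possible. The whole intake endpoint is not compromised, since T1 and T4 are free of this error, and the primary endpoint and sample size are untouched. The change is worth making because it is cheap and because dish identity that is not recorded on the diary days may be hard to recover later.

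**What to change.** Amend the nutritional-intake paragraph of Section 6.1.2 to say:

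- FoodforCare dishes are coded from the supplier's recipe or product composition (protein and energy) for the dish as prepared for that patient, multiplied by the portion actually eaten as recorded in the diary.
- The patient notes the dish name or label in the diary, so that the dietician can match it during the cross-check already planned.
- All other foods, in both arms, are coded with the national table.
- The coding rules are fixed before analysis.

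The portion must be the one eaten, not the one supplied. Section 1 treats plate waste as a known issue, and coding the delivered portion would inflate meal-arm intake.

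Cost: a composition list covering protein and energy has to be obtained from the supplier, and the dietician has slightly more coding work. No visits are added.

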3. STUDY DESIGN

A randomized controlled trial will be performed in palliative abdominal oncology patients at home. Inclusion will take place at the department of Medical Oncology at the start of palliative chemotherapy. The study is intended to be performed from March 2017 to July 2018. Patients will be randomly assigned to one of two groups before the start of the second cycle of chemotherapy because it is expected that FoodforCare at Home will make the largest difference during this cycle. The intervention group will receive meals from FoodforCare at Home and the control group will continue their regular diet for three weeks from the second cycle of chemotherapy until the next cycle of chemotherapy. Before the start of this study, a pilot study will be performed to determine whether the intervention is feasible in terms of logistics and delivery of the meals for example.

Measurements will take place at four time points during the study period i.e. before the start of chemotherapy, at the 2nd cycle of chemotherapy, at the 3rd cycle of chemotherapy and three month after T3 (figure 1). These measurements will be performed by AYA's/research assistants who will visit the patients at home. Time point 1, before the start of chemotherapy, will serve as the baseline measurement. At this moment, informed consent will be obtained and signed by the patient and the MUST score will be determined. Quality of life of patient and caregiver, nutritional intake, nutritional status, functional status and medication use will be assessed at all time points. For quality of life, the EORTC-QoL-C30 questionnaire will be filled in by the patients and the Caregiver Reaction Assessment by their caregivers. Nutritional status will be assessed using the handgrip strength measurement, the PG-SGA and performance scale by means of the Karnofsky score and the SPPB. Data on nutritional intake will be recorded using a 3-day food diary, which the patients will fill in by themselves. Medication use will be obtained from the patient's medical file. Additionally, during the intervention period, patients will record their symptoms using 'Utrecht Symptoom Dagboek' and medication use will be assessed by using a diary. At time point 3, patient satisfaction in the intervention group will be assessed by the Net Promoter Score with additional questions. An overview of the measurements can be found in table 1.

Figure 1. Flowchart of the study design of the FoodforCare at Home study.

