4.4 Sample size calculation

The sample size calculation is based on the primary outcome of this study: the EORTC-QoL-C30 questionnaire for quality of life. The primary outcome of this study is the difference in quality of life between the 2 groups at the start of the 3rd cycle of chemotherapy. Based on literature, advanced cancer patients with gynecological tumors and tumors of the colon have a mean score of approximately 60 points with a standard deviation of 22 points on the EORTC-QoL-C30 questionnaire. Assuming a difference of 10 points, on a scale of 0-100 points, is a clinically relevant difference in favor of FoodforCare at Home, we estimate that 76 patients are needed in each group in order to obtain a power of 80% (two-tailed t-test, alpha=0.05). Assuming a drop-out rate of 20%, this means a total of 180 patients. In order to improve the power significantly, we will make use of the ANCOVA test [31]. By multiplying the number of patients with $(1-(\rho^2))$ a total of 164 patients will be needed. The correlation between the baseline and follow-up outcome T2 (ρ) is estimated at 0.3.

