6.4 Withdrawal of individual subjects

6.4.1 Specific criteria for withdrawal

Subjects can end their participation in the study at any time for any reason if they wish to do so without any consequences. The investigator can decide to withdraw a subject from the study for urgent medical reasons.

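### The Net Promoter Score has a stated range that does not match its groups, and it is asked only at T3, so intervention patients who leave earlier are never scored

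*Combined protocol and SAP*

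**What the plan says.** Section 6.1.2 (Patient satisfaction) gives the range and the groups of the NPS in one sentence: "The score ranges from 1-10 and patients can be grouped in 'promoters' (9-10 grading), 'passively satisfied' (7-8 grading) and 'criticasters' (0-6 grading"). The formula is then "The NPS is finally calculated by subtracting the percentage of criticasters from the percentage of promoters".

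On who is asked and when, section 6.1.2 says that the NPS "will be used to assess patient satisfaction in the intervention group at time point 3". Section 3 agrees: "At time point 3, patient satisfaction in the intervention group will be assessed by the Net Promoter Score with additional questions". Table 1 marks patient satisfaction only at the 3rd cycle. Controls receive a different questionnaire, on wellbeing, shopping and cooking.

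On leaving early, section 6.4.1 says: "Subjects can end their participation in the study at any time for any reason if they wish to do so without any consequences". Section 4.4 plans for losses: "Assuming a drop-out rate of 20%, this means a total of 180 patients". It gives neither timing nor reasons for them. Section 6.5 provides for extra recruits to make up for withdrawals. Section 6.6 mentions use of data only for withdrawal after T3. Section 8.1 applies intention-to-treat to all analyses. No section says what happens to the satisfaction score of a patient who leaves before T3.

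**The concern.** There are two separate defects in one endpoint definition.

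First, the range and the lowest group cannot both be right. Whoever prints the form from section 6.1.2 has to guess whether 0 is offered.

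Second, the formula uses percentages of those who answer at T3. A patient who gives up the meals and leaves the study in the first week drops out of both numerator and denominator. That patient's opinion is among the most informative for a satisfaction score, and the plan has no means of recording it. Replacement recruits under section 6.5 restore the number of answers but not the missing opinions.

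The NPS is the only named satisfaction score for the meals, and secondary objective 7 concerns satisfaction. What is at stake is how far the reported NPS describes everyone who was given the meals. The primary outcome is not affected.

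**Working it through.** The documents give no expected NPS, target or benchmark, so there is no planned figure to reproduce. The check asks how far each defect could move the score.

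**Inputs**
- Groups 9-10, 7-8 and 0-6, stated range 1-10, and NPS = % promoters - % criticasters (section 6.1.2).
- 164 patients randomised into two groups (section 5.1). The ratio is not stated; 1:1 is assumed, giving 164/2 = 82 per arm.
- Drop-out 20% (section 4.4). That all of it falls before T3 is an assumption, so 10% and 30% are shown as well.
- Illustrative observed NPS of +20, from 40% promoters and 20% criticasters (assumed).

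**1. Range mismatch**

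*Same digit, with a would-be 0 recorded as 1.* Both are criticasters, so nobody changes group. The shift is exactly 0.

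*Linear conversion of a 0-10 answer x to 1 + 0.9x.* 6 becomes 6.4, 7 becomes 7.3, 8 becomes 8.2 and 9 becomes 9.1. After rounding, nobody changes group. The shift is 0.

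*Would-be 0 answers left blank.* With a uniform spread over the 11 points, the NPS goes from (2 - 7)/11 = -45.5 to (2 - 6)/10 = -40.0. Two skewed example distributions move from +16.0 to +19.6 and from -66.0 to -59.5. The rise is about 4 to 7 points.

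*Patients divide their opinion u (0 to 1) evenly over the classes offered.* On 0-10, NPS = P(u > 9/11) - P(u < 7/11). On 1-10, NPS = P(u > 0.8) - P(u < 0.6). For assumed shapes of u:

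| Shape of u | 0-10 form | 1-10 form | Shift |
|---|---|---|---|
| Beta(2,4) | -93.3 | -90.6 | +2.7 |
| Uniform | -45.5 | -40.0 | +5.5 |
| Beta(2,2) | -61.2 | -54.4 | +6.8 |
| Beta(4,2) | -17.7 | -7.4 | +10.2 |
| Beta(6,2) | +16.1 | +26.5 | +10.3 |
| Beta(5,2) | +0.6 | +11.1 | +10.5 |
| Beta(7,2.5) | +9.0 | +20.3 | +11.3 |

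Shifts are taken before rounding. The effect therefore runs from 0 to about +11 points, and anything above 0 needs an assumption about how patients use the scale.

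**2. Patients unscored before T3**

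With a proportion m unscored, full-arm NPS = (1 - m) × NPS of those scored + m × NPS of leavers. At m = 0.20 this is 0.20 × 82 = 16.4 leavers and 65.6 scored. With +20 among those scored, 0.8 × 20 = 16, and then:
- all leavers criticasters: 16 + 0.2 × (-100) = -4
- half criticasters, no promoters: 16 + 0.2 × (-50) = +6
- all passively satisfied: 16 + 0 = +16
- same as those scored: 16 + 0.2 × 20 = +20
- all promoters: 16 + 0.2 × 100 = +36

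The extreme bounds are 8 to 28 at m = 0.10 (18 ± 10) and -16 to 44 at m = 0.30 (14 ± 30).

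For comparison, the standard error of the observed score is √[(0.40 + 0.20 - 0.20²)/65.6] = √(0.56/65.6) = 0.092, or 9.2 points. The step from +20 to -4 is 24/9.2 = 2.6 standard errors, and the step from +20 to +36 is 16/9.2 = 1.7. A confidence interval computed from the T3 answers alone would not reflect this uncertainty.

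**The case against.** A reader might infer that both features inflate the score and so favour FoodforCare. The documents do not support that.

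- **Range.** The cut-offs 7 and 9 are the same digits on either form, and a missing 0 falls into the same group. The form itself is not in the documents; it may already run 0-10, with 1-10 a slip in the text. The 11-point figure rests on assumed response behaviour and assumed distributions of opinion.
- **Leavers.** The 20% has no stated timing. Some of it may fall between inclusion and randomisation, or in the three months after T3. Section 4.4 does tie the sample size to the 3rd cycle, so loss before T3 is possible, but it is not stated. In patients on palliative chemotherapy, leaving may follow progression, toxicity or death and have nothing to do with the food. Leavers could be as satisfied as stayers, or more so. Patients who stop the meals but remain in the study could still be asked at T3; nothing excludes them.
- **Consequence.** No target or threshold depends on the NPS, and section 6.1.2 adds further satisfaction questions beside it.

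All of this stands, and it limits the point to a small one with no proven direction. It does not remove the contradiction in the definition or supply a score for patients who leave before T3.

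**Conclusion.** The point holds as a minor one. The definition contradicts itself and should be corrected, though the mismatch has no necessary effect on the score. The T3-only collection leaves early leavers unscored and can bias the NPS. Upward is the plausible direction, because dissatisfied patients have a reason to leave, but the documents do not establish it. Under 1:1 allocation, all 20% lost before T3 and an observed +20, the full-arm value lies between -4 and +36. If fewer are lost between first delivery and T3, the range narrows in proportion (8 to 28 at 10%).

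A related inconsistency belongs to the same edit. Section 8.3 plans an independent-samples t-test of patient satisfaction between the groups, but the NPS exists in one group only and controls answer a different questionnaire. That test cannot be carried out on the NPS.

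**What to change.** 1. In section 6.1.2, state the range as 0-10 so that it matches the 0-6, 7-8 and 9-10 groups, and check that the printed form agrees.
2. In sections 3 and 6.1.2 and in Table 1, ask the NPS question at T3 or when the patient stops the meals or withdraws, whichever comes first. It is one question, asked at the last delivery visit or by telephone.
3. Report the NPS over intervention patients who received at least one delivery, and give the number randomised who received none, since section 8.1 promises intention-to-treat throughout. Report the number unscored with reasons, and bounds in both directions: all unscored as criticasters and all as promoters. A lower bound alone would count a patient who died or progressed as dissatisfied with the food.
4. Reconcile section 8.3 with section 6.1.2: either name a satisfaction item that both groups answer and test that, or drop the between-group test and describe the NPS in the intervention arm with a confidence interval.

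The cost is one corrected figure, one question asked earlier by staff who already visit these patients, and a few lines of text. The downsides are small: some leavers will decline, answers will come from slightly different times, and the reported NPS may be lower.
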